The compact nature of Matlab makes a simple sampling design practical and efficient. The small geographical area, compared to more dispersed study regions, removes the need for any kind of multiple stage cluster sampling. The **primary sample** of the MHSS (as opposed to the other three components of the MHSS, the DNFS followup sample, the Outmigrant sample and the Community sample) will consist of a probability sample of 2717 baris in the Matlab surveillance area in both the treatment and comparison areas. The bari is the basic unit of social organization in rural Bangladesh and in Matlab in particular. Baris usually consist of a cluster of households linked in many instances in a kin network-(note however that about 16% of baris consist only of a single household and even in multi-household baris, kin networks may exist only for sub-clusters of households). Sampling baris rather than households provides a better representation of family networks, a major focus of the program project, and gives us the opportunity to collect data on common bari resources. Within each bari, we will select upto two households for detailed interviews and within households we will interview selected respondents.

Key features in the proposed sample design for the **primary sample** are as follows:

- o The sampling design will be a stratified random sample with the bari as the primary sampling unit (PSU). The allocation of sample size to strata will be proportional to the number of baris in the strata. The Matlab region will be divided into two roughly equal strata (in terms of households and baris): (1) Matlab treatment area; (2) Matlab comparison area. For bari level analyses the sample will be self-weighting.
The sample of baris will be drawn from the DSS 1994 sample frame. Baris will be randomly sampled from the treatment and comparison frame. In each bari we will obtain information on bari-level characteristics from a knowledgeable member or members of the bari (we recognize the possibility that there may be subclusters of households within the bari, and we may need the help of more than one individual to get the core bari information).
In addition to getting bari level information, we will sample up to two households in each bari. The net (interviewed) sample will thus consist of 2717 baris and 5000 households.

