The development of weights for sub-bari data elements: The proposed primary sampling units are the bari's. Sampling proportional to number of bari's within the two family planning regions (treatment and comparison) produces a self weighting sample for bari level analysis. As we consider the sampling stages within the bari the weights get a bit more complicated. The first stage of within bari sampling is the selection of households. The second stage is the selection of adults within households. The third stage is the selection of children of the adults. The calculation of sampling probabilities is facilitated by the detailed Matlab household rosters.

The probability of selecting a particular household is the sum of the probabilities of selecting the household first and second. For example, in bari's with more than two households every household has a probability of $1/(\text{number of households})$ of being selected first. The probability of a household being selected second is a more complicated. It is a function of the relationships between the households and the sampling rules. For example, if you are the father of the first sampled household's head you are sampled with conditional probability one given the first household was sampled. However, you could also be sampled second if another household is sampled first by the same or a different sampling rule. All of the probabilities of the ways you could be sampled second must be added up and then added to the probability that you are sampled first to get your household's overall sampling probability. Although a bit complicated these probabilities can be calculated from the bari rosters. In summary, the probability of selecting any given household is $p(\text{selecting the bari}) * p(\text{selecting the household given the bari is selected})$. Weights for household level analysis are proportional to the reciprocal of this probability.

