We will consider the power of the primary sample alone. The power with the DNFS/outmigrant sample incorporated will be even larger when such an incorporation is appropriate. From our experience with the IRMS, we have selected an outcome measure to explore the power of this design, general health status (GHS). For adults in IRMS GHS had a mean of 1.9 and a standard deviation of .64. If we wish to detect a difference in GHS for two groups that split the population roughly equally, for example treatment area vs comparison area, the power to detect a difference of .05 (or less than 1/12 of a standard deviation) is 38%. At a difference of .1 (or less than 1/6 of a standard deviation) the power is up to 96%. The effective sample size for other levels of analyses are larger but must be adjusted for design effects. For example, the sample will have almost twice as many households as baris. However with a large clustering effect ($\rho = .25$) the effective sample size would be only 60% larger. Never-the-less the power would still be larger than the already substantial bari level power. Multivariate modeling will typically reduce the clustering by the inclusion of explanatory variables resulting in even larger effective sample sizes.

SURVEY INSTRUMENTS

Bari and Household Questionnaires

Table 3 summarizes the modules of the questionnaire to be administered at the bari, household and individual levels. In the subsequent paragraphs we describe in detail the content of the different modules of the questionnaire.

	Sample baris	Sampl ehhs	0-14	15-49 Male	15-49 Female	50+ Mal e	50+ Female
Expected # of respondents	2717	5000	7463	4388	4779	2840	2328
Control Card	X	X					
Bari Module	X						
Household Module		X					
Health & Physical Performance				X	X	X	X
Life History-(mstat,educ,work, inc,mig,nres-kin)				X	X	X	X
Fertility					X		X
Child Characteristics					X		X
Anthropometrics			X	X	X	X	X
Cognitive Ability			X	X	X	X	X
Physical Activity & Diet					X		

****Note:** In addition to the primary sample above, 900 households will be interviewed as part of the DNFS sample and 600 households as part of the Outmigrant sample. In both the DNFS outmigrant samples, the same within household selection procedure will be followed, with the caveat that the DNFS woman and the outmigrant individual will always be selected. The bari questionnaires will be administered only where applicable (i.e. in rural areas).

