3) Human subjects will be recruited from a study population which is followed by the Matlab Demographic Surveillance System, under the aegis of the International Centre for Diarrhoeal Disease Research, Bangladesh (ICDDR,B). ICDDR,B is a non-profit research organization funded by 14 countries, with the largest sponsor being the United States. The Matlab Demographic Surveillance System has been collecting bi-weekly information on vital events (births, deaths, migrations and marriages) for approximately 192,000 individuals in about 40,000 households since the mid 1960s-- (a computerized linked file is available since 1974). In addition there is also computerized information available from two censuses in 1974, 1982 and a host of specialized studies conducted on sub-groups of this study population-- (see Summary Research Plan, Tables, 2, 3).

Signed consent forms in Bangla, will be obtained by interviewers from all community, bari and household respondents, with parents/guardians acting as proxies for respondents below the age of 15. The consent form will briefly outline the nature of the questions and the objectives of this data collection effort; it will specify that participation is completely voluntary with no penalty for not consenting to the interview and that respondents may choose not to answer/or participate in any section of the survey if it makes them uncomfortable ; it will emphasize that the information will be completely confidential and will be used only for research purposes; it will inform the respondents that certain prior basic demographic data collected by the Matlab surveillance system and by other specialized studies about the respondents may be incorporated into this dataset; and finally that respondents may be involved in followup interviews-(for which separate consent will be taken).

It is important to note that there will be absolutely no element of coercion for the MHSS. We expect high response rates based on a number of factors. First there is excellent rapport between the interviewers and the respondents as the interviewers are all locally recruited. Second, the questions are unlikely to be

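### The 60% gain in household-level effective sample size assumes two households in every bari; the plan's own counts give about 50%, and the figure leaves out the loss from the planned household weights

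*Protocol*

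**What the plan says.** All of this stands in the Protocol, mostly in Section D.

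- **Sample size** (Sample Design, key features): "The net (interviewed) sample will thus consist of 2717 baris and 5000 households". The overview of the same part notes that "about 16% of baris consist only of a single household".
- **Household selection** (same list): every household is taken in baris of one or two. In larger baris two are taken, the first at random and the second by kin preference.
- **Weights** (Properties of Sample Design, weights for sub-bari data): "Weights for household level analysis are proportional to the reciprocal of this probability", that is, the probability that the household is selected.
- **Power** (Properties of Sample Design): the bari-level calculation is presented as the least favourable one. For households the text says that "the sample will have almost twice as many households as baris". It continues "However with a large clustering effect", with rho set at .25, and concludes that "the effective sample size would be only 60% larger". It then adds: "Never-the-less the power would still be larger than the already substantial bari level power".
- **Population** (Section E, item 3): "approximately 192,000 individuals in about 40,000 households". Section A states that the 2717 baris are a 33 percent sample of all baris.

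**The concern.** The power text says almost twice as many households but appears to compute with exactly two per bari, which contradicts the plan's own counts. It also warns that other levels of analysis need adjusting for design effects, and then adjusts for clustering only. Because two households are taken from a large bari whatever its size, the prescribed weights grow with bari size, and unequal weights cost precision.

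Two statements rest on the figure: that household-level power exceeds bari-level power, and that the bari level is the least favourable case. If the weighting loss is large enough, neither is guaranteed for a weighted household estimate.

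**Working it through.** **Inputs from the Protocol.** 2717 baris; 5000 households; rho = .25; 16% single-household baris; 33% bari sampling fraction; about 40,000 households; standard deviation of general health status .64.

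**1. The printed figure.** With m households per bari, the effective number per bari is m/(1 + (m − 1)rho). For m = 2 this is 2/1.25 = 1.600, or 1.600 × 2717 = 4,347. This is the printed 60%.

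**2. The plan's own counts, clustering only.**
- Mean households per bari: 5000/2717 = 1.840.
- Single-household baris: 2 × 2717 − 5000 = 434, or 16.0%, which agrees with the stated share. The other 2283 give two each.
- Size-weighted cluster size: (434 + 4 × 2283)/5000 = 9566/5000 = 1.913.
- Design effect: 1 + 0.913 × .25 = 1.228.
- Effective households: 5000/1.228 = about 4,071. Ratio to baris: 4,071/2717 = 1.498.

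Two variants agree closely. The plain mean gives 1.840/1.210 = 1.521. Summing information over baris gives 0.16 + 0.84 × 1.6 = 1.504. The gain is 50% to 52%.

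**3. Adding the planned weights.** Total baris are about 2717/.33 = 8,233, so mean bari size is about 40,000/8,233 = 4.86. Assume equal selection chance within a bari. A household then has weight 1 in a bari of one and H/2 in a bari of H ≥ 2. Per sampled bari, the effective number is

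ratio = (mean H)² / [0.16 + 0.84 × 0.625 × E(H² | H ≥ 2)],

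where 0.625 = (2 + 2 × .25)/4. The mean size of multi-household baris is (4.86 − 0.16)/0.84 = 5.59. For fixed mean and share of singles, the ratio is largest when these baris are all nearly the same size, here a mix of 5 and 6:

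4.86² / (0.16 + 0.84 × 0.625 × 31.5) = 23.6/16.7 = 1.41.

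This ceiling needs no assumed shape and is insensitive to the rounded inputs: mean sizes from 3 to 6 give 1.41 to 1.45. Below it, the result depends on the spread of bari sizes. The shapes in this table are assumptions:

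| Size of multi-household baris | Ratio | Gain | Effective households |
|---|---|---|---|
| Near-constant (ceiling) | 1.412 | +41% | 3,836 |
| Poisson-like | 1.278 | +28% | 3,472 |
| Negative binomial, shape 4 | 1.170 | +17% | 3,179 |
| Negative binomial, shape 2 | 1.080 | +8% | 2,934 |
| Geometric-like | 0.935 | −7% | 2,540 |
| Negative binomial, shape 0.7 | 0.838 | −16% | 2,277 |

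The gain vanishes when E(H² | H ≥ 2) = (23.6 − 0.16)/0.525 = 44.6, which is a standard deviation of √(44.6 − 5.59²) = about 3.7 around 5.59. Simulating one assumed kin structure lowered the results further: about +20% (Poisson-like), +1% to +2% (shape 2) and −11% to −13% (geometric-like).

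**4. Effect on power for a difference of .05.** The Protocol states no alpha. At two-sided .05, bari-level power is 53%. Household-level power is 73% at +60%, 70% at +50%, 63% at +28% and 50% at −7%. At two-sided .02, which reproduces the Protocol's 38% for baris (38.6%), the corresponding values are 60%, 57%, 49% and 36%.

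**The case against.** The arithmetic slip is small. Effective size drops from 4,347 to about 4,071, some 6%, and power from 73% to 70% at two-sided .05. At +50% the Protocol's conclusion about household power still holds. The figure is offered as an example with a deliberately large, hypothetical rho; with 1.84 households per bari, a rho of about .16 would give 60%. No sample size is derived from it. All of that stands, and it limits the weight of the point.

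The weighting part rests on loose inputs: 40,000 and 33% are rounded, and Section A dates the 16% to 1982, whereas the frame is from 1994. The loss applies to weighted estimates, and an unweighted model-based analysis would not bear it in full. That stands too.

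A reader might infer that the plan's own weights reduce the gain to a definite figure, or that household-level power is in fact below bari-level power. The documents support neither. They give no bari-size distribution and no weight variance. Of the six shapes tried with equal selection chance, four keep household power above bari power and only the two most skewed reverse it. Nor is the plan silent on weighting: it defines weights for household, adult and child analyses.

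The objection does not rescue the 60%. It contradicts the plan's counts at the stated rho, and the weighted ceiling of about 41% lies below it.

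**Conclusion.** The concern holds in two parts of different strength. First, the printed 60% is wrong at the stated rho. The plan's own counts give about 50% (50% to 52% by method), or about 4,070 effective households, with no outside assumption. Second, the example leaves out the loss from the prescribed weights. With mean bari size about 4.86, 16% singles and equal selection chance within the bari, the weighted gain cannot exceed about 41%. How far below that it lies is unknown from the documents; the range from +28% to −16% is a set of scenarios, not an estimate.

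The statements that household power is larger and that the bari level is the least favourable case are therefore unassured for weighted analyses, not refuted. The correction is worth making because a stated precision figure is too favourable and the frame to settle it exists.

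**What to change.** In the paragraph on power of the sample design:

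1. Replace 60% by about 50% for clustering alone at rho = .25, and name the mix of one- and two-household baris behind it.
2. Add the household-level effective size with the planned weights, computed from the 1994 DSS bari-size distribution and the selection probabilities, including the kin rules. If those probabilities are not yet available, give the result under equal selection chance and say so.
3. Qualify, without deleting, the sentence that household-level power is larger and the description of the bari level as the least favourable case. For weighted analyses both depend on the calculation in step 2.

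The cost is one calculation on an existing frame and a few sentences. The design and sample size do not change; a stated figure becomes less favourable.

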RAND places a strong emphasis on thorough testing of survey instruments and field procedures before fieldwork begins. Although the development process can seem lengthy, we have found that it invariably improves the instrument and quality of field procedures and leads to considerable cost savings by averting last-minute changes in content and protocol. In addition, questionnaire development takes on a special importance when a team of researchers is working in a culture to which not all are indigenous. RAND's experience in Malaysia and Indonesia has repeatedly demonstrated the value of following an explicit program of questionnaire design, testing and field procedure testing. Because the survey instrument will be complex, we will use a wide array of development techniques, including small-scale pilot interviews, focus groups, and larger pretests; [name] and [name] will participate in all phases. One considerable advantage is that [name], is a native speaker of Bangla and has extensive experience working with data from the Matlab area. (please see the Budget Justification for further details).

PREPARING FOR AND FIELDING THE SURVEY: A major advantage of working with ICDDR,B is that in addition to their existing field staff, ICDDR,B maintains a pool of experienced part-time interviewers used for specialized surveys. All are area residents with a high school education (or higher) and have an existing rapport with the sample population.

In addition to [name] and [name] who will observe and participate in training and quality control, ICDDR,B will combine its existing field and new employees to provide the following personnel. There will be 24 teams in the field responsible for collecting household/bari/community level information for the primary sample, the DNFS sample, the outmigrant sample and the community sample. Each team will consist of a male interviewer, a female interviewer, a measurement specialist (this individual will be responsible for all anthropometrics, physical performance tests and cognitive tests), and a porter to help carry equipment. There will be a total of six junior supervisors (one for every four teams) and three senior supervisors (one for every eight teams). In addition the field co-ordinator-([name]) will oversee the field operations. Thus there will be a total of 106 field staff of which 48 are interviewers, 24 are measurement specialists/testers, 24 are porters, and 10 are supervisors (with 6 junior, 3 senior and 1 overall field-coordinator). The high supervisor to team ratio is justified by the burden of quality control, editing and assignment of households that will be placed on supervisors.

We estimate that each interviewing team will on average be able to complete two households a day (the project schedule is included in the Budget Justification). Because of the bari-level clustering, small travel distances and the experienced field staff we believe this is a reasonable goal. In many cases we expect that the interview will require more than one visit to the household. Because of bari-level clustering, however, interviewing teams will be able to work efficiently by rotating among households in a bari until all interviews are complete, thereby reducing travel time between revisits. **Our plans for selection and training of field staff, quality control and production monitoring are described in the Budget Justification.**

DATA ENTRY, PROCESSING, AND DOCUMENTATION: It is important that the data produced by the survey be available at the earliest possible time. Computer-assisted data entry will allow immediate checks on the data for consistency and logic, thereby reducing lag time between data collection and data processing. Completed questionnaires will be sent on a daily basis from the field office to the central ICDDR,B office in Dhaka (there are two trips every day in each direction) where the data will be entered on PCs, checked, batch-edited and prepared for analysis. This daily transfer will ensure that the data entry process is continuous, so that errors can be caught early on. [name] will assist in developing basic cleaning and editing routines that will permit early detection of most errors so that they can be handled while the survey is still in the field. Further data file preparation, particularly the processing of life histories, will be undertaken at RAND. Bari-level, household-level and individual-level identifiers will be linked, allowing for demographic

and economic analyses of family relationships, such as transfers.

An important aspect of the data cleaning and documentation process is the assessment of the reliability of the data. We will perform descriptive analyses of data quality, focusing especially on the retrospective data. These will include analyses of representativeness and non-sampling errors such as recall bias. Performing these analyses will enable us to better document the data and alert users to potential quirks. We will also investigate which types of respondents have high rates of item non-response (e.g., those with no schooling). This will alert users to the possibility that non-response is selective with respect to variables of interest in a particular analysis.

Finally, the project will produce documentation for the MHSS consisting of several publications. A codebook, including questionnaires and interviewer instructions, and a user's guide will be prepared describing the data. We will also produce: (1) a technical report describing sampling and survey methods and response rates, (2) a report presenting basic descriptive results for the major survey topic areas along with analyses of sample selectivity and response error. **Further information on data entry and documentation is found in the Budget Justification.**

E. HUMAN SUBJECTS:

It should be noted that this research project has already undergone human subjects review at RAND and has been approved on condition of an approved Data Safeguarding Plan and further Human Subjects Protection Committee (HSPC) review if funded. The HSPC serves as RAND's Institutional Review Board to review federally funded research involving human subjects, as required by 15 federal departments and agencies, including the Departments of Health and Human Services (HHS), Justice, Education, and Defense. RAND's "Multiple Project Assurance of Compliance" (#M1031) with HHS regulations (45 CFR 46) also serves as our assurance of compliance with the regulations of the other federal departments and agencies. (Please refer to IRB number and approval date on face page).

The International Centre for Diarrhoeal Disease Research, Bangladesh (ICDDR,B) will perform the proposed data collection (in this research project) under subcontract to RAND. While RAND is the primary grantee, the Center for Population Studies at the University of Pennsylvania will also be involved in the research project.

1) We propose to design and field a major household and community survey in Matlab, a region of rural Bangladesh that forms part of an ongoing Demographic Surveillance System. This survey, the Matlab Health and Socio-economic Survey or MHSS will be linked to existing demographic, surveillance information and other past studies in the Matlab area. The data collection will address the following broad areas of concern: the effect of socio-economic and behavioral factors on adult survival, health status, and health care utilization; the linkages between elderly wellbeing, kin characteristics and intergenerational resource flows; and the impact of community services and infrastructure on adult health and other human capital acquisition.

The MHSS will consist of four distinct sample components:

- (i) The Primary sample consisting of 5000 households, clustered in 2717 baris. This represents a 33 percent sample of the total number of baris in the Matlab Surveillance area.
- (ii) The Determinants of Natural Fertility Survey (DNFS) sample consisting of a followup of 900 households of women originally interviewed about their health and pregnancy status in the mid 1970s. This represents approximately a 40% sample of the surviving 2183 DNFS women.
- (iii) The Outmigrant sample consisting of the households of 300 female and 300 male outmigrants who have left the households of the primary sample between 1982 and the date of the MHSS and not returned. This represents approximately a 10% sample of outmigrants who have left since 1982.
- (iv) The Community sample consisting of information on community infrastructure and services and detailed data on 500 health/family planning providers, and health, family planning and educational facilities potentially serving (in the opportunity set of) the primary sample households in the MHSS. This constitutes a census of schools, health and family planning clinics serving the study population and a sample of individual health/family planning providers.

Respondents in the MHSS will include representation from all age, gender, and ethnic/religious groups relevant to this population. Pregnant women and children will be interviewed as part of this survey as one of the major foci of this survey is fertility outcomes and human capital investments in children.

The key socio-demographic characteristics of the primary sample of the MHSS are presented in Table 2 and 3 of the Project 1 proposal and are summarized below in Table 4;

Age	Male	Female
0-14	3849	3614
15-49	4388	4779
50+	2840	2328
Total	11,077	10,721

The age and gender distribution of the DNFS followup sample and the outmigrant sample are difficult to estimate precisely. However there is sure to be adequate representation of both genders and all age groups. In addition to the household/family sample this survey will also collect information by questionnaire on community infrastructure and services and health, family planning, and educational facilities and providers.

2) We will accumulate data on the human subjects through the following means:

- (i) questionnaires as part of the survey;
- (ii) measurements (anthropometrics, cognitive tests and physical performance tests) as part of the survey; and
- (iii) linking of pre-existing computerized data-records from the Matlab surveillance system.

The survey (including the measurements) is expected to take about four hours per household to complete. All the data collected as well as the pre-existing data incorporated into the MHSS will be used for exclusively research purposes.

3) Human subjects will be recruited from a study population which is followed by the Matlab Demographic Surveillance System, under the aegis of the International Centre for Diarrhoeal Disease Research, Bangladesh (ICDDR,B). ICDDR,B is a non-profit research organization funded by 14 countries, with the largest sponsor being the United States. The Matlab Demographic Surveillance System has been collecting bi-weekly information on vital events (births, deaths, migrations and marriages) for approximately 192,000 individuals in about 40,000 households since the mid 1960s-- (a computerized linked file is available since 1974). In addition there is also computerized information available from two censuses in 1974, 1982 and a host of specialized studies conducted on sub-groups of this study population-- (see Summary Research Plan, Tables, 2, 3).

Signed consent forms in Bangla, will be obtained by interviewers from all community, bari and household respondents, with parents/guardians acting as proxies for respondents below the age of 15. The consent form will briefly outline the nature of the questions and the objectives of this data collection effort; it will specify that participation is completely voluntary with no penalty for not consenting to the interview and that respondents may choose not to answer/or participate in any section of the survey if it makes them uncomfortable ; it will emphasize that the information will be completely confidential and will be used only for research purposes; it will inform the respondents that certain prior basic demographic data collected by the Matlab surveillance system and by other specialized studies about the respondents may be incorporated into this dataset; and finally that respondents may be involved in followup interviews-(for which separate consent will be taken).

It is important to note that there will be absolutely no element of coercion for the MHSS. We expect high response rates based on a number of factors. First there is excellent rapport between the interviewers and the respondents as the interviewers are all locally recruited. Second, the questions are unlikely to be

considered sensitive and will (if history is any guide) be perceived to be of some possible value in indirectly affecting the future welfare of individuals in general. Third, there is a general sense of good feeling towards ICDDR,B (the parent organization of the Matlab Demographic Surveillance System) as it provides an array of health and family planning services free of charge to this study population. **Moreover access to and use of these services is explicitly not contingent on cooperation with the surveillance.** Fourth, the study population is used to being interviewed as part of the surveillance system. A recent baseline survey carried out in connection with the ICDDR,B-BRAC collaboration had a response rate of over 99%.

Finally, this research project will have to undergo human subjects review at RAND (mentioned above) and at ICDDR,B if it is funded. The review guidelines at ICDDR,B are modeled after the Health and Human Services(HHS) guidelines in the United States.

4 and 5) While there is the possibility of some social embarrassment, in this kind of comprehensive survey, it is very unlikely as no really sensitive information will be elicited. Similar questions have been successfully asked in this population without any problems. Furthermore individuals will be informed of their right to refuse to answer any portion of the questionnaire that they are uncomfortable with. Respondents will also be informed of the confidentiality of their responses.

An important concern in the release of any public-use data set is the protection of respondents' privacy. We will take extensive precautions to ensure that respondents are unable to be identified. Confidentiality will be strictly maintained at ICDDR,B, the proximate survey group. In addition identifiers on public release data will not be the original ICDDR,B 'ids'. A second set of 'ids' will be created that map to the original ICDDR,B 'ids'. This mapping will be maintained in the strictest privacy (including restricted access to data files and keeping hard copy in locked files) at RAND, the University of Pennsylvania and ICDDR,B, the institutions involved in the survey. No identifying information will be released to any private or government group. Finally survey protection policies will have to be approved and monitored by the Human Subjects Committee independently at ICDDR,B and at RAND.

The Physical Performance Tests which involve measurements of gait, balance and limb strength have potentially some risk of physical injury from falling as a result of going-off balance. This risk however is minimal. A strict screening protocol will be followed, which ensures that the measurement specialist gauge the ability of the respondent (both by questions and tester's assessment) to successfully complete the tests, before they are administered. The nature of the tests (sitting up from a chair height cube, standing, walking) are such that minimal physical discomfort is involved. At no time will the respondent be at any risk of physical injury or risk. Survey team members will make sure that no respondent is in any danger of falling or hurting themselves in any way. As mentioned before, all respondents will be explicitly queried as to their understanding of the test procedures and their ability to comply without discomfort. Respondents will be reminded of the voluntary nature of the tests and their right to refuse to participate without any penalty. Extensive interviewer training in ensuring respondent safety will be carried out.

6) The risks (as described in sections 4 and 5) to the respondent population are minimal and very reasonable vis a vis the expected benefits from this data collection which will yield hitherto unavailable information on individual, household and family decision making in a resource poor environment. This knowledge has applications beyond this study population.

F. VERTEBRATEANIMALS:

Not Applicable

G. CONSULTANTS:

The Consultants on this project are:

Anthropologist	ICDDR,B
[name]	RAND
[name]	UPENN
[name]	RAND
[name]	RAND
[name]	UPENN
[name]	RAND
[name]	ICDDR,B
[name]	ICDDR,B
[name]	ICDDR,B

Their time on this project has been included in the budget. For further details, see project description and budget justification.

H. CONTRACTUALARRANGEMENTS:

See Summary Research Plan section I.

I. LITERATURE CITED

Andrews, G. R., A. J. Esterman, A. J. Braunack-Mayer, and C. M. Rungie, "Aging in the Western Pacific," Manila: *World Health Organization Regional Office for the Western Pacific*, 1986.

Annotated Bibliography of ICDDR,B. 1990. Studies in Matlab, Bangladesh. Specialized Bibliography Series No. 14. *International Centre for Diarrhoeal Disease Research, Bangladesh*. Dhaka, Bangladesh, 1990.

